#### **Observational Cohort**

Demographics and baseline characteristics will be listed with respect to the start of Study 115B overall using all subjects enrolled in the Observational Cohort.

#### 12.3.2.3 Prior and Concomitant Medications

Medications used in this study will be coded by using the World Health Organization Drug Dictionary Enhanced and categorized as the following:

- **Prior medication:** medication continued or newly received before initial dosing of study drug in the previous study.
- **Post-treatment medication**: any medication continued or newly received after the end of the Treatment-emergent Period of the Cumulative Study Period
- Concomitant medication: medication continued or newly received during the Treatment-emergent Period of the Cumulative Study Period.

A given medication can be classified as a prior medication, concomitant medication, or a post-treatment medication; both concomitant and post-treatment; both prior and concomitant; prior, concomitant, and post-treatment. Incidence of prior medication will be summarized based on the 116 Safety Set by 1) preferred name; 2) anatomic class (ATC) level 1; ATC level 2; and preferred name.

Incidence of concomitant medication as well as the exposure adjusted number of concomitant medication will be summarized based on the Safety Set for the Cumulative Study Period by 1) preferred name; 2) ATC level 1; ATC level 2; and preferred name.

All medications in the Cumulative Study Period will be listed for each subject.

## 12.3.2.4 Study Drug Exposure and Compliance

#### **Study Drug Exposure**

Duration of study drug exposure is defined as follows: last dose date of the Cumulative Study Period – first dose date of the Cumulative Study Period + 1 day, regardless of any dose interruptions.

Duration of study drug exposure as well as number of sticks administered defined as (total number of sticks dispensed) – (total number of sticks returned) will be summarized descriptively overall based on Safety Set for the Cumulative Study Period. Additionally, the total duration of treatment exposure, defined as the sum of the subject's duration of treatment exposure and expressed in subject-years, will be provided. Duration of exposure will also be summarized as a categorical variable.

## **Study Drug Compliance**

Study drug compliance will be calculated as follows:  $100 \times (1 - [total number of days of study drug interruption in the Cumulative Study Period] / [duration of study drug exposure in the Cumulative Study Period). The total number of days of study drug interruption is defined as the$ 

sum of (number of days of each study drug interruption in the Cumulative Study Period), where number of days of each study drug interruption is defined as the interruption end date – the corresponding interruption start date + 1.

Treatment compliance percentages will be summarized descriptively (number, mean, SD, median, minimum, and maximum) overall based on Safety Set for the Cumulative Study Period. The number and percentage of subjects whose compliance is <80% or ≥80% will be summarized.

- 12.3.3 Pharmacodynamic Analysis
- 12.3.3.1 Analysis of Primary Variables

Not applicable

- 12.3.3.2 Analysis of Secondary Pharmacodynamic Endpoints
- 12.3.3.2.1 Absolute Change from Baseline: Sweat Chloride, BMI, BMI-for-Age Z-score, Weight, Weight-for-Age Z-score, Stature, Stature-for-Age Z-score, and LCI

For the secondary endpoint of sweat chloride, raw and absolute change from the Cumulative Study Baseline in sweat chloride at each visit in the Cumulative Study Period (including all measurements from Study 115B and Study 116, including the Safety Follow-up Visit of Study 116, both on-treatment measurements and measurements after treatment discontinuation), will be summarized based on FAS. Descriptive statistics including number of subjects, mean, SD, SE, median, minimum, and maximum, along with the 95% CI and within-group *P* value based on Normal approximation, will be provided for the absolute change from the Cumulative Study Baseline. The mean (95% CI) of the absolute change from baseline will be plotted. The following secondary endpoints will be summarized similarly as described above for sweat chloride based on FAS:

- Absolute change from Cumulative Study Baseline in BMI and BMI-for-age z-score
- Absolute change from Cumulative Study Baseline in weight and weight-for-age z-score
- Absolute change from Cumulative Study Baseline in stature and stature-for-age z-score
- Absolute change from Cumulative Study Baseline in LCI2.5
- Absolute change from Cumulative Study Baseline in LCI5.0

# 12.3.3.2.2 Analysis of Pulmonary Exacerbation-related Other Secondary Pharmacodynamic Variables

• Time-to-first pulmonary exacerbation: Time-to-first pulmonary exacerbation, defined as days from study drug initiation in the previous study to first pulmonary exacerbation, will be analyzed using Kaplan-Meier method based on Safety Set for the Cumulative Study Period. Cumulative incidence of pulmonary exacerbation will be summarized and plotted. Subjects without an exacerbation will be considered censored at the end date of the Cumulative Study Period.

- Number of pulmonary exacerbations: The number of pulmonary exacerbations starting during the Cumulative Study Period (including both on-treatment events and events after treatment discontinuation), normalized by the time spent in the Cumulative Study Period (last date in the Cumulative Study Period first date in the Cumulative Study Period + 1), will be summarized for the Cumulative Study Period.
- Number of CF-related hospitalizations through last visit: For number of CF-related hospitalizations occurring during the Cumulative Study Period, the analysis will be similar to the analysis of number of pulmonary exacerbations.

## 12.3.3.2.3 Absolute Change in FE-1 Levels From Baseline

Raw values and absolute change from Cumulative Study Baseline in FE-1 levels at each visit in the Cumulative Study Period will be summarized descriptively based on FAS, similar to sweat chloride.

## 12.3.3.2.4 Absolute Change in Serum Levels of IRT From Baseline

Raw values and absolute change from Cumulative Study Baseline in IRT at each visit in the Cumulative Study Period will be summarized descriptively based on FAS, similar to sweat chloride.

## 12.3.3.2.5 Change in Microbiology from Baseline

Raw values and absolute change from Cumulative Study Baseline in microbiology at each visit in the Cumulative Study Period will be summarized descriptively based on FAS, similar to sweat chloride. Percentage of subjects with cultures positive at each visit in the Cumulative Study Period will be summarized descriptively based on the FAS for each possibly-detected organism.

Additional analysis may be added in the SAP, if any.

### 12.3.4 Safety Analysis

The overall safety profile of study drug will be assessed in terms of the following safety and tolerability endpoints:

- Incidence of treatment-emergent adverse events (TEAEs)
- Clinical laboratory values (serum chemistry, hematology, coagulation studies, and urinalysis)
- ECGs (standard 12-lead)
- Vital signs
- Pulse oximetry
- OEs
- Spirometry (subjects ≥3 years age at screening in Study 115B)

The safety analysis will be based on the Safety Set. All listings will be provided based on the All Subjects Set.

#### 12.3.4.1 Adverse Events

For analysis purposes, AEs will be classified as pretreatment AEs, TEAEs, or post-treatment AEs.

- Pretreatment AEs: AEs occurred before initial dosing of study drug in the previous study.
- **TEAE:** any AE that increased in severity or that was newly developed during the Treatment-emergent Period of the Cumulative Study Period.
- **Post-treatment TEAE:** any AE that increased in severity or that was newly developed after the end of the Treatment-emergent Period of the Cumulative Study Period.

AEs with missing or partial start dates, if there is no clear evidence that the AEs started before or after study treatment, then the AEs will be classified as TEAEs.

All TEAE summaries will be described, using number and percentages of subjects, as well as number of events per 100 patient-years (number of events adjusted for the total duration of exposure) for the Cumulative Study Period. An overview of the TEAE profile will be provided, including total number of TEAEs, with number and percentage of subjects as well as number of events per 100 patient-years for the following categories: (1) all TEAEs; (2) Grade 3/4 TEAEs; (3) TEAEs by relationship; (4) TEAEs by maximum severity; (5) TEAEs leading to treatment interruption; (6) TEAEs leading to treatment discontinuation; (7) serious TEAEs; (8) related serious TEAEs; and (9) TEAEs leading to death.

AE summary tables will be presented for TEAEs only and will include the following:

- All TEAEs
- Grade 3/4 TEAEs
- TEAEs by relationship
- TEAEs by maximal severity
- TEAEs leading to treatment interruption
- TEAEs leading to treatment discontinuation
- Serious TEAEs
- Related serious TEAEs
- TEAEs leading to death
- Frequently reported TEAEs

Summaries will be presented by MedDRA system organ class (SOC) and preferred term (PT) using frequency counts and percentages and number of events per 100 patient-years (i.e., number and percentage of subjects with an event as well as exposure-adjusted number of events). When summarizing the number and percentage of subjects with an event, subjects with multiple occurrences of the same AE or a continuing AE will be counted once, only the maximum severity level will be presented in the severity summaries, and the worst/highest relationship

level in the relationship summaries. In addition, listings containing individual subject data for all TEAEs leading to treatment interruption, TEAEs leading to treatment discontinuation, deaths, and SAEs will be provided separately. All AEs, including pre- and post-treatment AEs, will be presented in individual subject data listings.

A listing of SAEs for the Observational Cohort will be provided based on all subjects enrolled in the Observational Cohort.

### 12.3.4.2 Clinical Laboratory Assessments

For the laboratory measurements, the raw values and change from Cumulative Study Baseline of the continuous hematology and chemistry results will be summarized in SI units at each visit in the Cumulative Study Period.

For hematology and chemistry, the number and percentage of subjects with abnormal low (<lower limit of normal [LLN]) value and with abnormal high (>ULN) value at each scheduled time point in the Cumulative Study Period will be summarized.

The number and percentage of subjects with at least 1 categorical change during the Treatmentemergent Period of the Cumulative Study Period will be provided.

The categorical criteria will be provided in the SAP.

Results of urinalysis will be listed in individual subject data listings only. In addition, a listing containing individual subject hematology, chemistry, and coagulation values outside the reference ranges will be provided. This listing will include data from scheduled and unscheduled time points.

## 12.3.4.3 Electrocardiogram

For the ECG measurements, a summary of raw values and change from Cumulative Study Baseline values will be provided at each scheduled time point of the Cumulative Study Period, for the following standard digital ECG measurements: PR, QT, and QT corrected for HR (QTc) intervals (Fridericia's correction [QTcF = QT/RR $^{1/3}$ ], QRS duration, and HR. In addition, the mean value at each time point will be plotted for QTcF.

The number and percentage of subjects with at least 1 categorical change during the Treatment-emergent Period of the Cumulative Study Period will be summarized.

The categorical criteria will be provided in the SAP.

The number and percentage of subjects with shift changes from Cumulative Study Baseline (normal/missing, not clinically significant, and potentially clinically significant according to overall ECG evaluation) to the worst ECG evaluation during the Treatment-emergent Period of the Cumulative Study Period will be summarized.

### **12.3.4.4** Vital Signs

For the vital signs measurements, the raw values and change from Cumulative Study Baseline values will be summarized at each scheduled time point of the Cumulative Study Period: systolic and diastolic blood pressure (mm Hg), body temperature (°C), pulse rate (beats per minute), and respiratory rate (breaths per minute).

The number and percentage of subjects with at least 1 categorical change during the Treatment-emergent Period of the Cumulative Study Period will be summarized.

The categorical criteria will be provided in the SAP.

## 12.3.4.5 Pulse Oximetry

For the pulse oximetry measurements, a summary of raw values and change from Cumulative Study Baseline values will be provided at each scheduled time point of the Cumulative Study Period for the percent of oxygen saturation by pulse oximetry.

The number and percentage of subjects with shift changes from Cumulative Study Baseline (normal/missing and low according to the reference range) to the lowest percent of oxygen saturation during the Treatment-emergent Period of the Cumulative Study Period will be summarized.

## 12.3.4.6 Ophthalmological Examinations

OE findings will be presented as a data listing.

## 12.3.4.7 Spirometry

Spirometry data will be summarized descriptively at each visit based on the Safety Set for subjects who are ≥3 years of age at screening in Study 115B. The raw values and absolute change/relative change from Cumulative Study baseline values will be summarized at each scheduled time point of the Cumulative Study Period.

## 12.3.4.8 Physical Examination

PE findings will be presented as a data listing only.

### 12.3.4.9 Other Safety Analysis

Not applicable

## 12.3.5 Interim and IDMC Analyses

## 12.3.5.1 Interim Analysis

No interim analysis is planned but interim analyses may take place at any time during the study if warranted by the ongoing data, and/or deemed necessary by the internal Vertex team.

## 12.3.5.2 IDMC Analysis

Details of the IDMC (Section 9.1.5) analysis will be provided in the IDMC Analysis Plan.

## 13 PROCEDURAL, ETHICAL, REGULATORY, AND ADMINISTRATIVE CONSIDERATIONS

# 13.1 Adverse Event and Serious Adverse Event Documentation, Severity Grading, and Reporting

#### 13.1.1 Adverse Events

#### 13.1.1.1 Definition of an Adverse Event

An AE is defined as any untoward medical occurrence in a subject during the study; the event does not necessarily have a causal relationship with the treatment. This includes any newly occurring event or worsening of a pre-existing condition (e.g., increase in its severity or frequency) after the ICF is signed.

An AE is considered serious if it meets the definition in Section 13.1.2.1.

## 13.1.1.2 Clinically Significant Assessments

Study assessments including laboratory tests, ECGs, PEs, and vital signs will be assessed and those deemed to have clinically-significant worsening from baseline will be documented as an AE. When possible, a clinical diagnosis for the study assessment will be provided, rather than the abnormal test result alone (e.g., urinary tract infection, anemia). In the absence of a diagnosis, the abnormal study assessment itself will be listed as the AE (e.g., bacteria in urine or decreased hemoglobin).

An abnormal study assessment is considered clinically significant if the subject has 1 or more of the following:

- Concomitant signs or symptoms related to the abnormal study assessment
- Further diagnostic testing or medical/surgical intervention
- A change in the dose of study drug or discontinuation from the study

Repeat testing to determine whether the result is abnormal, in the absence of any of the above criteria, does not necessarily meet clinically significant criteria. The determination of whether the study assessment results are clinically significant will be made by the investigator.

A laboratory value that is Grade 4 will not automatically be an SAE. A Grade 4 laboratory value will be an SAE if the subject's clinical status indicates a life-threatening AE.

#### 13.1.1.3 Documentation of Adverse Events

All AEs will be collected from the time the ICF is signed until the following time points:

- Withdrawal of consent
- For enrolled subjects who have a Safety Follow-up Visit: through the Safety Follow-up Visit
- For enrolled subjects who do not have a Safety Follow-up Visit, the earliest of
  - o 18 days after the last dose of study drug, or
  - o the ETT Visit, if that visit is 10 days or later following the last dose of study drug (see Section 9.1.2.3)

NOTE: Only SAEs will be collected for the Observational Cohort.

All subjects will be queried, using nonleading questions, about the occurrence of AEs at each study visit. When possible, a constellation of signs and/or symptoms will be identified as 1 overall event or diagnosis. All AEs for enrolled subjects will be recorded in the CRF and source document. AEs for subjects who are screened but not subsequently enrolled in the study will be recorded only in the subject's source documents. The following data will be documented for each AE:

- Description of the event
- Classification of "serious" or "nonserious"
- Date of first occurrence and date of resolution (if applicable)
- Severity

- Causal relationship to study drug(s)
- Action taken
- Outcome
- Concomitant medication or other treatment given

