Event/Assessment a	Day 1 d	Day 3 (± 1 Day)	Day 15 (± 3 Days)	Weeks 12, 24, 36, 48, 60, 72, 84 (± 7 Days)	Week 96 (± 7 Days)	As Soon as Possible After the Last Dose	2 Weeks (± 4 Days) After the Last Dose	
Medications, treatments, and		Continuous from signing of ICE through Sofety Follow, un Visit (if required)						
Adverse events		Continuous from signing of ICF through Safety Follow-up Visit (if required)  Continuous from signing of ICF through Safety Follow-up Visit (if required)						

AE: adverse event; BMI: body mass index; ECG: electrocardiogram; ETT: Early Termination of Treatment; ICF: informed consent form; IVA: ivacaftor; LCI: lung clearance index; LUM: lumacaftor; OE: ophthalmological examination; PE: physical examination; q12h: every 12 hours

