### 9.1.1 Timing of Study 116 Day 1 Visit

#### 9.1.1.1 Treatment Cohort and Observational Cohort

For subjects at sites activated by the time of their applicable Study 115B visit (i.e., the Safety Follow-up Visit for subjects in the Treatment Cohort and the Week 24 Visit or the Safety Follow-up Visit, if required, for subjects in the Observational Cohort), their Study 116 Day 1 Visit will be on the same day as their applicable Study 115B visit, and any Study 116 Day 1 assessments that were specified to be performed at the applicable Study 115B visit do not need to be repeated. If the Study 116 Day 1 Visit does not coincide with the subject's applicable Study 115B visit, the subject will complete all Study 116 Day 1 assessments (except the OE if it was performed within the last 3 months before the visit for subjects in the Treatment Cohort).

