### 9.1.1.2 Treatment Cohort

Subjects at sites activated by the time of their applicable Study 115B visit (Section 9.1.1.1) may return within 1 calendar day to complete the remaining Day 1 assessments specific to Study 116 (including administration of the Day 1 dose). Predose vital sign and spirometry assessments must be repeated before dosing on the following calendar day.

Subjects who were enrolled but had Day 1 LUM/IVA administration procedures (Section 9.6) delayed more than 1 calendar day will repeat all assessments that were specified to be performed at the Day 1 visit before receiving their first dose of LUM/IVA (except for the OE if it was performed within the last 3 months before the visit).

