### 9.5.2 Prior and Concomitant Medications

It is recommended that subjects remain on a stable medication regimen for their CF from Study 115B through the Safety Follow-up Visit in Study 116. Stable medication regimen is defined as the current medication regimen for CF that subjects have been following for at least 28 days before Day 1 of Study 115B.

Subjects who are using a bronchodilator should have their LCI and spirometry assessments performed according to the guidelines provided in Section 11.6.7.

Information regarding all prior and concomitant medications, including the subject's CF medications, other medications, and herbal and naturopathic remedies administered at, or after, the Safety Follow-up Visit in Study 115B through the Safety Follow-up Visit of this study will be recorded in each subject's source documents. In addition, concomitant medication dose(s) may be collected.

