### 9.2 Cumulative Study Period

The **Cumulative Study Period** starts from the first dose date of study drug in Study 115B to the last day in Study 116, regardless of

- 1) the planned 2-week Washout Period in Study 115B; and/or
- 2) the rollover gap between Study 115B and Study 116 (if any).

For subjects not enrolled in Study 116, the Cumulative Study Period will start from the first dose date of study drug in Study 115B to the last day in Study 115B.

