### **10.3.2.6 Analysis of Pulmonary Exacerbation-related Other Secondary Pharmacodynamic Variables**

**Time-to-first pulmonary exacerbation:** Time-to-first pulmonary exacerbation, defined as days from study drug initiation in the Study 115B to first pulmonary exacerbation, will be analyzed using Kaplan-Meier (KM) method based on the FAS for the Cumulative Study Period. Cumulative incidence of pulmonary exacerbation will be summarized for the overall group. Subjects without an exacerbation will be considered censored at the end date of the Cumulative Study Period.

**Number of pulmonary exacerbations:** The number of pulmonary exacerbations starting during the Cumulative Study Period (including both on-treatment events and events after treatment discontinuation), normalized by the time spent in the Cumulative Study Period (last date in the Cumulative Study Period – first date in the Cumulative Study Period + 1), will be summarized for the overall group based on the FAS.

**Number of CF-related hospitalizations through last visit:** The number of CF-related hospitalizations occurring during the Cumulative Study Period (including both on-treatment events and events after treatment discontinuation), normalized by the time spent in the Cumulative Study Period (last date in the Cumulative Study Period – first date in the Cumulative Study Period + 1), will be summarized for the overall group based on the FAS.

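### When rollover is delayed, the gap counts as observed time for exacerbations and hospitalizations, but Study 116 sets no look-back for events in it

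*Protocol*

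**What the plan says.** **Start of AE collection.** Protocol 13.1.1.3 states: "All AEs will be collected from the time the ICF is signed until the following time points". The AE definition in 13.1.1.1 is limited in the same way; it covers a new event or "worsening of a pre-existing condition (e.g., increase in its severity or frequency) after the ICF is signed". SAE reporting (13.1.2.2) also begins at consent, and Table 3-1 places consent on Day 1.

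**Delayed rollover.** Protocol 9.1.1.1 provides for the case "If the Study 116 Day 1 Visit does not coincide with the subject's applicable Study 115B visit". The child then completes the full Day 1 assessments, apart from a recent eye examination. No maximum interval is given. Protocol 9.1.1.2 deals separately with "Subjects who were enrolled but had Day 1 LUM/IVA administration procedures" delayed by more than one calendar day. That delay falls after consent.

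**Medications.** Protocol 9.5.2 reaches back across the gap: it records medications "administered at, or after, the Safety Follow-up Visit in Study 115B through the Safety Follow-up Visit of this study". The medications row of Table 3-1, repeated in SAP Appendix A, starts at consent instead, so the two passages disagree.

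**Exacerbations and hospitalizations.** Table 3-1 marks other outcome events on Day 1, and footnote v defines these as exacerbations, antibiotic therapy and hospitalizations. Protocol 11.4.4.1 and 11.4.4.2 describe the queries but give no date from which events should be recalled.

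**Time counted.** Protocol 12.2 and SAP 9.2 run the Cumulative Study Period straight through the 115B washout and any delay (in the SAP's words, "the rollover gap between Study 115B and Study 116 (if any"). Under SAP 10.3.2.6, exacerbation and CF-hospitalization counts are "normalized by the time spent in the Cumulative Study Period", taken as last date minus first date plus 1. Children without an exacerbation are censored at the end of that period. Protocol 12.3.3.2.2 has the same rules.

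**The concern.** Event collection and the time denominator run on different clocks. Suppose a child is hospitalized after the 115B Safety Follow-up Visit and before Study 116 consent. Under 9.5.2 the antibiotic is recorded. Study 116 has no SAE for the admission. Whether an exacerbation or hospitalization is counted depends on how far back the site happens to ask on Day 1. The antibiotic alone does not settle it, because the definition in 11.4.4.1 also needs one List A sign or two List B signs around the course, and nothing tells sites to reconstruct these for the gap. Medical history does not fill the hole, because 11.2 takes it from the previous study.

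The gap days nevertheless stay in the denominator. Missed events with retained time can only push the rates down. Time to first exacerbation could be lengthened for a child whose first event falls in the gap and is missed. Neither document plans to report how many children had a gap or how long it was, so a reader of the results could not judge the effect. Because long-term safety is the primary objective, it also matters that a serious event in that interval has no stated route into the Study 116 database.

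**Working it through.** **1. The uncovered interval.** For AEs and SAEs it runs from the 115B Safety Follow-up Visit to the Study 116 consent, not to the first Study 116 dose. A dosing delay after consent is inside the collection window.

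**2. The plan's own figures.** The only derived design number is expected enrollment: 56 × (1 − 0.10) = 50.4, stated as 50. The plan gives no figure for the frequency or length of gaps, so both are assumptions below.

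**3. Planned cumulative time without a gap.** This is 24 weeks in 115B, a 2-week washout and 96 weeks in Study 116, or 122 weeks. A 2-week Safety Follow-up in Study 116, where required, makes it 124 weeks.

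**4. Formulas.** Let g be the gap in weeks, T₀ = 122 or 124, and c the fraction of gap events captured.
- Gap share for an affected child: s = g / (T₀ + g).
- With a constant true rate λ, reported rate = λ × [1 − (1 − c) × s]. With c = 0 the understatement equals s.
- Share of pooled cohort time if a fraction f of children have a gap: f·g / (T₀ + f·g).

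**5. Results.**

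| Assumed gap | Child's share, T₀ = 124 | Child's share, T₀ = 122 | Cohort share, f = 0.25 (T₀ = 124; 122) |
|---|---|---|---|
| 4 weeks | 4/128 = 3.1% | 4/126 = 3.2% | 1/125 = 0.8%; 1/123 = 0.8% |
| 12 weeks | 12/136 = 8.8% | 12/134 = 9.0% | 3/127 = 2.4%; 3/125 = 2.4% |
| 26 weeks | 26/150 = 17.3% | 26/148 = 17.6% | 6.5/130.5 = 5.0%; 6.5/128.5 = 5.1% |

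These are upper limits, reached only if no gap event is captured. With half captured (c = 0.5), a 12-week gap understates that child's rate by 0.5 × 8.8% = 4.4%.

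**6. Kaplan-Meier.** A child with an exacerbation before the gap is unaffected, because the first event is already counted. A child without one stays in the risk set through the gap. If the first event falls there and is missed, the time is recorded as longer, or as censored.

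**7. Which analyses are touched.**
- Exacerbation and CF-hospitalization rates and time to first exacerbation (SAP 10.3.2.6): affected, because they use the Cumulative Study Period.
- The protocol's cumulative TEAE rates: affected, because the treatment-emergent period (12.2), the exposure duration (12.3.2.4) and the TEAE definition (12.3.4.1) all span the gap.
- The SAP's TEAE tables (SAP 9.1, 10.5 and 10.5.1): unaffected, because they start at the first Study 116 dose and gap events cannot enter them.

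**The case against.** A reader might infer that AEs in the gap are collected by neither study. The documents do not establish that. The 115B protocol is not among them, and 13.1.1.3 governs Study 116 only. A stop at the 115B Safety Follow-up Visit is plausible by analogy with Study 116. The same analogy would bring in 13.1.2.2, which requires drug-related SAEs after the Safety Follow-up Visit to be reported to the sponsor. Such events might therefore still reach the sponsor through 115B.

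A reader might also infer that exacerbations and hospitalizations in the gap are lost, so that the rates are certainly biased. That goes too far. These events are asked about on Day 1, 11.4.4.2 asks for dates and reasons without tying the query to consent, and a question about past events naturally looks back. What is missing is the start of the recall period.

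Nor does the text show that sites would restart drug unaware of gap events. Eligibility is reviewed before enrollment (Protocol 8), an exclusion covers comorbidities or laboratory abnormalities that could add risk (8.2), and a non-coinciding Day 1 brings the full set of assessments.

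Finally, the SAP allows that there may be no gap at all, the endpoints are descriptive secondary ones, and the cohort effect is small unless gaps are long or common. All of this stands and limits the size of the point. It does not supply a look-back, and it does not take unascertained days out of the denominator.

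**Conclusion.** The point holds at modest size. Study 116 does not collect AEs or SAEs between the 115B Safety Follow-up Visit and its own consent. If 115B stops collection at that visit, which these documents do not show, then neither study does, except possibly for drug-related SAEs. Ascertainment of exacerbations and hospitalizations in the gap is undefined rather than absent, while the gap is counted in full as observed time.

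The possible bias has one direction: lower rates, and a longer time to first exacerbation for a child whose first event is missed in the gap. The percentages rest on assumed gap lengths, a constant event rate, zero capture and, at cohort level, a quarter of children having a gap. On that basis the effect is at most about 3% to 17% for an affected child and 1% to 5% for the cohort. This is worth correcting because it is cheap, not because it threatens the main safety tables, which the SAP's choice of analysis period leaves untouched.

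**What to change.** **Protocol and CRF.** When Day 1 does not coincide with the 115B Safety Follow-up Visit, record after consent all SAEs, hospitalizations, and antibiotic courses with their List A and List B signs since that visit. Use the start date that 9.5.2 already sets for medications, and flag the events as off-drug gap events. Reconcile 9.5.2 with the medications row in Table 3-1 and SAP Appendix A.

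**SAP 9.2 and 10.3.2.6.** For any child without this look-back, exclude gap days from the rate denominators and from Kaplan-Meier time at risk. Report the number of children with a gap and the distribution of its length.

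**Cost.** One protocol sentence, a CRF flag at a visit that under 9.5.2 already takes a medication history over the same interval, and a short SAP addition. If data collection can no longer change, the SAP part alone still corrects the denominator. The downside is imperfect recall over a long gap.
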